## 6.9. Appendix 9: Definition for Persistent-Recurrent Hypoglycemia

[figure not shown]
A P-R hypoglycemia based on programming search in the e-diary of hypoglycemic events that meet prespecified criteria is defined as a set of hypoglycemic episodes that:

a) starts with the occurrence of a Level 3 or Level 2 hypoglycemic episode (<54mg/dL, [3.0 mmol/L]) and is followed by more episodes of hypoglycemia (<70mg/dL, [3.9 mmol/L]), within the day of the initial episode,

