#### Hypoglycemia

A participant's dose may be decreased based on hypoglycemia at any time during the study (Sections 6.5.1 and 6.5.2).

Do not increase the study intervention dose if hypoglycemia (BG  $\leq$ 70 mg/dL) is reported in the week prior to the assessment.

Although hypoglycemia criteria for dose reduction are specified in the tables for each treatment in Sections 6.5.1 and 6.5.2, it is important for the investigator to rule out any other contributing factors, such as increased physical activity or illness, which may cause an unusual occurrence of hypoglycemia. In these circumstances, the decision to reduce the dose is at the discretion of the investigator.

Study participants will be instructed to check their BG, when they experience signs and symptoms suggestive of hypoglycemia, and to administer appropriate treatment for when BG ≤70 mg/dL (3.9 mmol/L). They will be instructed to recheck BG levels 15 minutes following treatment of hypoglycemia and repeat treatment and BG recheck after another 15 minutes until the BG level has returned to the target range of 80-130 mg/dL (4.4-6.6 mmol/L) (CDC 2021). Instructions will be provided for clinical management of participants who experience frequent or repeated hypoglycemia. As necessary, additional instruction/education may be provided to participants by investigative staff, including increased BG monitoring, treatment adjustments, or other approaches (for example, behavioral interventions and lifestyle modification) to mitigate hypoglycemia frequency or severity.

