#### 8.1.1.1. Self-Monitoring of Blood Glucose (SMBG)

#### Glucometer for participant use during the study

Participants will receive a sponsor-approved glucometer and related testing supplies for use during the study.

Site personnel will train the participant on correct use of the glucometer for self-monitoring blood glucose and reporting of hypoglycemia data in the e-diary.

Participants should use the glucometer

- for the 6-point profile
- whenever hypoglycemia is experienced or suspected

• Note: If BG values are <80 mg/dL but not below <70 mg/dL (that is, defined as hypoglycemia), recommend to the participant that they monitor their BG more frequently to prevent hypoglycemia. This is particularly relevant to participants receiving LY3209590 via the autoinjector, where dose cannot be adjusted precisely to meet glycemic requirements.

- when there is awareness of increased risk related to changes in dietary intake, physical activity, or inadvertent or atypical insulin dosing
- to check for hyperglycemic events, or
- as directed by the investigator.

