#### 4.6.2.1.2. Persistent-Recurrent Hypoglycemia

The potential risk of persistent-recurrent hypoglycemia (P-R hypoglycemia) will be assessed from the first dose date up to the end of the study and will be based on two approaches to identify persistent-recurrent hypoglycemic events:

- 1. using investigator assessment and clinical judgment to determine if repeated hypoglycemia may have contributed to a hypoglycemic event that degenerated with poor outcomes, and
- 2. using a prespecified criteria to derive events from e-diary database (see definition in Appendix 10 (Section 6.9).

Identification of P-R hypoglycemia based on investigator reporting is precipitated by a hypoglycemic event a participant or their caregiver inform having resulted in a poor outcome. This information will trigger an e-mail alert notifying the investigator to contact the study participant, obtain more information about the specific hypoglycemic event, and provide them clinical guidance, if appropriate. Hypoglycemic events that trigger alerts to investigators are those participants or caregivers report in the e-Diary have required treatment with glucagon or IV glucose, resulted in coma, motor vehicle accident or other trauma, hospitalization, or emergency medical care.

Upon receiving the e-mail notification, investigator will access the e-Diary database and answer the following question: "In your clinical judgement, is this hypoglycemia event associated with repeated hypoglycemia events?". Investigator should select "Yes" or "No" as an answer.

During protocol training, investigators are trained to consult the e-Diary database and review participant's blood glucose values and hypoglycemia reports to determine the best answer. If investigator judges the hypoglycemic event that triggered an alert is related to repeated episodes of hypoglycemia, the participant will be identified as having presented a P-R hypoglycemic event reported by the investigator.

P-R hypoglycemia events and participants who present P-R hypoglycemia will be identified by one or both approaches explained above. Summary statistics and a listing of the events identified by both methods will be provided.

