## 4.6.3. Additional Safety Assessments

## 4.6.3.1. Participant-Reported Hypoglycemic Events

The following types of hypoglycemia events will be derived in the analysis data sets: documented hypoglycemia as Level 1, Level 2, and Level 3 (severe hypoglycemia) according to definitions based on the American Diabetes Association criteria where:

- Level 1: glucose <70 mg/dL (3.9 mmol/L) and ≥54 mg/dL (3.0 mmol/L);
- Level 2: glucose <54 mg/dL (3.0mmol/L);
- Level 3: severe hypoglycemia (confirmed by the investigator to be an event that required assistance for treatment).

Level 2 and Level 3 events are considered clinically significant hypoglycemia. Therefore, the analysis on a composite of Level 2 and Level 3 (denoted as Level 2/3) hypoglycemia will also be conducted.

The hypoglycemia will also be further classified into

- nocturnal hypoglycemia (occurs between midnight and 0600)
- non-nocturnal hypoglycemia (occurs between 0600 and midnight)

If a hypoglycemic event is within 60 minutes of another hypoglycemic event, it is considered as a continuation of the previous event. If there are multiple hypoglycemic events within 60 minutes of each other, then all events will be combined into a single event, which has the

- earlier date time
- minimum glucose value, if applicable
- maximum severity (Level 1, 2 or 3)
- combined symptoms and outcomes, and
- time of nocturnal if any of the events is nocturnal

of the multiple hypoglycemic events.

The combined event starts from the first records with Level 1, 2 or 3, and ends when there are no more events for at least 60 minutes.

The evaluation of potential persistent-recurrent hypoglycemia events will be through assessment of the clinically significant events confirmed by investigators based on clinical judgment and through events identified by a pre-specified criteria described in Section 4.6.2.1.2 and Appendix 9 (Section 6.9) using information based on the participant-reported hypoglycemia.

The details of planned analyses are provided in the below table.

Endpoint	Analysis Period*	Statistical Method
Event rate of Level 1	Baseline, 0-16, 0-26, 0-52, 16-26,	Negative binomial regression with
hypoglycemia events	26-52 weeks, post-treatment period	treatment and baseline HbA1c as
(events/participant/year):		covariates, log (exposure/365.25
All documented		days) as the offset in the model.
Event rate of Level 2	Baseline, 0-16, 0-26, 0-52, 16-26,	Negative binomial regression with

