**AND** 

b) is followed by at least one episode of hypoglycemia (<70mg/dL, [3.9 mmol/L]) per day, in the next 2 days or longer, and that ends when no hypoglycemia episode occurs for at least 2 days.

An example of a set of hypoglycemic episodes meeting the search criteria for a P-R hypoglycemia event is illustrated in the figure below.

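### If the programmed persistent-recurrent hypoglycemia search runs on merged events, a closely checked prolonged first-day low that recurs on the next 2 days can fail the definition, while the same low checked less often passes

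*SAP*

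**What the plan says.** SAP 4.6.2.1 lists P-R hypoglycemia as a safety topic of interest. Section 4.6.2.1.2 gives two routes to it, investigator judgment and a programmed e-diary search, and either is enough.

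The programmed rule is in SAP Appendix 9 (Section 6.9):

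- Criterion (a): the set starts with a Level 2 or 3 episode and "is followed by more episodes of hypoglycemia (<70mg/dL, [3.9 mmol/L]), within the day of the initial episode".
- Criterion (b), joined by AND: the set "is followed by at least one episode of hypoglycemia (<70mg/dL, [3.9 mmol/L]) per day, in the next 2 days or longer".

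Events are derived in SAP 4.6.3.1: "If a hypoglycemic event is within 60 minutes of another hypoglycemic event, it is considered as a continuation of the previous event". The combined event takes the "earlier date time" of its components and "ends when there are no more events for at least 60 minutes". There is no maximum duration. The same section says that the P-R criteria draw on the participant-reported hypoglycemia, and its table plans a Fisher's exact comparison of participants with at least one P-R event.

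Protocol 6.5 (Hypoglycemia) asks participants to recheck 15 minutes after treating a low and to "repeat treatment and BG recheck after another 15 minutes until the BG level has returned to the target range".

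Appendix 9 does not say whether an episode is the merged event, or whether a day is a calendar day or 24 hours. Its worked example is a figure that is not available here.

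**The concern.** Criterion (a) needs a second episode on the first day, but the merge rule removes second episodes when low readings lie close together. The protocol's 15-minute rechecks are well inside the 60-minute window, so a participant who stays low for hours and follows the instruction produces one merged event. If lows then recur on each of the next 2 days, (b) is met but (a) is not.

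The flag therefore depends on how often the participant tests as well as on the hypoglycemia. Extra low readings, which are more evidence of a prolonged low, can remove it. That is an awkward property for a safety topic whose name includes persistence, in a trial of an insulin with a half-life of about 17 days (Protocol 6.9). At stake is the face validity of the programmed count and of the between-arm comparison built on it.

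**Working it through.** The plan gives no expected count, rate or power for this definition, so there is no figure to reproduce. The check applies the written rules to constructed patterns.

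**Rules applied**
- Merge (SAP 4.6.3.1): a low reading less than 60 minutes after the previous low reading continues the event; the merged event keeps the earliest time and the lowest glucose. Gaps of exactly 60 minutes are left aside, because the two sentences of the rule can be read differently there.
- (a): a Level 2 episode followed by at least one more episode <70 mg/dL on day 0. This is the lenient reading of the plural in the text.
- (b): at least one episode on day 1 and on day 2.
- Any Level 2 episode may start the sequence.

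**Smallest case.** A Level 2 reading at 10:00 and a low at 11:15 are 75 minutes apart, so they are two events and (a) is met. Add a low reading at 10:40: the gaps are 40 and 35 minutes, all three merge into one event, and (a) is no longer met.

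**Constructed patterns** (day 0 is the first day)

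| Pattern | Records → merged events | Merged, calendar day | Merged, 24 h | Unmerged |
|---|---|---|---|---|
| 1. Low 10:00–14:00, every 15 min; one low on days 1 and 2 | 17 + 2 = 19 → 3 | not flagged | not flagged | flagged on both |
| 2. Low 10:00–14:30, every 90 min; one low on days 1 and 2 | 4 + 2 = 6 → 6 | flagged | flagged | flagged on both |
| 3. Level 2 at 23:30, Level 1 at 01:00; one low at 02:00 on days 2 and 3 | 4 → 4 | not flagged | flagged | 24 h only |
| 4. Low 23:00–02:00, every 15 min; one low at 12:00 on days 1, 2 and 3 | 13 + 3 = 16 → 4 | not flagged | flagged | flagged on both |
| 5. Level 2 at 23:30, Level 2 at 01:00, a low later on day 1, one low on days 2 and 3 | 5 → 5 | flagged | flagged | flagged on both |
| 6. Low 10:00–14:00, every 15 min, one day only | 17 → 1 | not flagged | not flagged | not flagged on either |

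**Reading the table**
- Patterns 1 and 2 are nearly the same low with the same recurrence. Only the testing interval decides the flag. Pattern 1 fails on either meaning of day, so this part does not rest on the calendar-day reading.
- Pattern 3 fails only if day means calendar day. Pattern 4 fails on merged calendar days because the whole event is dated to 23:00 on day 0.
- Pattern 5 crosses midnight and is still flagged, because the 01:00 Level 2 episode restarts the sequence.
- Pattern 6 fails on (b), whatever the merge does.

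**The case against.** The strongest reply is that the plan defines one construct, a set of episodes recurring over days, and never says that a single long low is the target. That stands for a low confined to one day (pattern 6). It does not answer pattern 1, where lows do recur on each of the next 2 days.

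Two premises are inferred. SAP 4.6.2.1.2 and Appendix 9 speak of searching the e-diary, which could mean unmerged records, and day could mean 24 hours. Both caveats stand, and the missing figure might settle them. Merged input remains likelier, because SAP 4.6.3.1 puts the merge in the event derivation and then links the P-R criteria to those data.

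Other outputs also capture these lows: Level 2/3 rates, incidence and mean cumulative functions, and the severe-event listing. Protocol 8.3.6 asks investigators whether repeated or prolonged episodes preceded a severe event. These limit the consequence but do not produce the P-R flag. The investigator route helps only in part: "Hypoglycemic events that trigger alerts to investigators are those participants or caregivers report in the e-Diary have required treatment with glucagon or IV glucose", or led to coma, trauma, hospitalization or emergency care. A prolonged, self-treated Level 2 low need not trigger it. The sensitivity analysis in SAP 4.6.3.1, which counts one event until glucose reaches 70 mg/dL or more, does not help: in a continuous low it joins readings however far apart they are.

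A reader might infer under-reporting in the LY3209590 arm, because Protocol 8.1.1.1 says of closer monitoring: "This is particularly relevant to participants receiving LY3209590 via the autoinjector". The documents do not support that step. The advice concerns glucose below 80 but not below 70 mg/dL; it does not set recheck spacing during a low, and the 15-minute instruction is the same in both arms. Closer monitoring can also reveal more separate lows and so raise the count. The net direction is unknown.

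**Conclusion.** The point holds as a gap in the definition, conditional on the search using merged events. On that reading, a prolonged first-day low checked at gaps under 60 minutes and followed by lows on each of the next 2 days is missed by the programmed search, while the same low checked at gaps over 60 minutes is found. The midnight issue is additional, affects only some sequences, and depends on day meaning calendar day.

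Its size cannot be stated. The patterns above are constructed, and the documents give neither the frequency of such sequences nor the spacing of readings. A reader might attach probabilities by assuming recheck gaps or onset times, but these would describe the assumptions and would not estimate missed events. Nor do the documents support saying that persistent or midnight-crossing events in general go uncounted: patterns 2 and 5 are flagged, and the investigator route is separate.

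The consequence is confined to an ungated safety summary with a Fisher's exact comparison. No primary or gated test is affected. The change is worth making because the defect is specific and cheap to remove.

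**What to change.** In SAP Appendix 9:

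1. State whether an episode is the merged event of Section 4.6.3.1, and define day.
2. Add a supplementary programmed count in which (a) is also met when the combined event containing the Level 2/3 record spans more than 60 minutes from first to last record <70 mg/dL, computed from the unmerged e-diary time stamps.
3. Leave (b) unchanged and report the present definition alongside.

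The 60-minute threshold is the SAP's own merge window, and it removes the dependence on testing. Take a Level 2 reading and a later first-day low more than 60 minutes apart. Either they stay separate and meet (a) by count, or intermediate lows join them and they meet (a) by span. Pattern 1 (span 240 minutes) and pattern 4 (span 180 minutes) would then be flagged in the supplementary count. Pattern 6 would still fail on (b), and pattern 3 depends on the definition of day.

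Moving (b) to consecutive 24-hour windows is not advised. With a Level 2 episode at 10:00 and a low at 15:00 on day 0, then lows at 09:00 on day 1 (23 hours after the start) and 11:00 on day 2 (49 hours), calendar days flag the sequence. The 24-to-48-hour window is empty, so 24-hour windows do not.

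The cost is SAP wording, a small programming change on time stamps already collected, one extra output line and possibly a few more flagged events. Nothing in participant management changes.

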**AND** 

b) is followed by at least one episode of hypoglycemia (<70mg/dL, [3.9 mmol/L]) per day, in the next 2 days or longer, and that ends when no hypoglycemia episode occurs for at least 2 days.

An example of a set of hypoglycemic episodes meeting the search criteria for a P-R hypoglycemia event is illustrated in the figure below.

# 6.10. Appendix 10: Abnormality Level Criteria for Chemistry and Hematology Laboratory Results

Parameter	Level 1	Level 2	Level 3
General Chemistry			
Sodium, low (mEq/L)	<132	<130	<125
Sodium, high (mEq/L)	>150	>155	>160
Potassium, low (mEq/L)	<3.6	<3.4	<3.0
Potassium, high (mEq/L)	>5.5	>6	>6.5
Chloride, low (mEq/L)	<95	<88	<80
Chloride, high (mEq/L)	>108	>112	>115
Bicarbonate, low (mEq/L)	<20	<18	<15
Bicarbonate, high (mEq/L)	N/A	N/A	>30
Blood urea nitrogen, high (mg/dL)	>23	>27	>31
Calcium, low (mg/dL)	<8.4	<8.0	<7.5
Calcium, high (mg/dL)	>10.5	>11.0	>12.0
Phosphate, low (mg/dL)	<2.5	<2.0	<1.4
Protein (total), low (g/dL)	<6.0	<5.4	<5.0
Albumin, low (g/dL)	<3.1	<2.5	<2.0
Uric Acid (urate), high (mg/dL)	>7.0	NA	NA
Kidney Function			
Creatinine, increase (mg/dL)	≥1.5 x baseline	≥2.0 x baseline	≥3.0 x baseline
eGFR, decrease (ml/min/1.73m 2 )	≥25% decrease	≥50% decrease	≥75% decrease
Lipids			
Cholesterol (total), high (mg/dL)	>200	>240	>300
HDL, low (mg/dL), males	<40	<30	<20
HDL, low (mg/dL), females	<50	<40	<20
LDL, high (mg/dL)	>130	>160	>190
Triglycerides, high (mg/dL)	>150	>300	>500

Parameter	Level 1	Level 2	Level 3
Hematology			
Complete Blood Count			
WBC, low (cells/μL)	<3500	<3000	<1000
WBC, high (cells/μL)	>10,800	>13,000	>15,000
Hemoglobin, decrease (g/dL)	N/A	>1.5 dec. from baseline	>2 dec. from baseline
Hemoglobin, increase (g/dL)	N/A	>2 inc. from baseline	>3 inc. from baseline
Platelets, low (cells/μL)	<140,000	<125,000	<100,000
Hemoglobin, low (g/dL), male	12.5-13.5	<12.5	<10.5
Hemoglobin, low (g/dL), female	11.0 - 12.0	<11	<9.5
WBC Differential			
Lymphocytes, low (cells/μL)	<1000	<750	< 500
Lymphocytes, high (cells/μL)	>4000	>10000	>20000
Neutrophils, low (cells/μL)	<2000	<1000	< 500
Eosinophils, high (cells/μL)	>650	>1500	>5000
Coagulation Studies			
Prothrombin time, increase (sec)	>1.1 x ULN	>1.3 x ULN	>1.5 x ULN

Abbreviations: eGFR = estimated glomerular filtration rate; HDL = high-density lipoprotein; LDL = low-density lipoprotein; WBC = white blood cell.

Note: For liver enzymes, Lilly defined categories will be used.

# 6.11. Appendix 11: Interaction Effect for Subgroup Analysis – Treatment Regimen Estimand

The ANCOVA analysis will be performed within each subgroup with multiple imputation of missing primary measures. Statistical inference over multiple imputation of missing data will be guided by Rubin (1987) to obtain  $\hat{\theta}_1$  and  $se(\hat{\theta}_1)$  for the treatment difference in subgroup 1, and  $\hat{\theta}_2$  and  $se(\hat{\theta}_2)$  in subgroup 2. Then, the distribution of treatment by subgroup interaction (difference of treatment effects) is:  $\hat{\theta}_1 - \hat{\theta}_2 \sim N\left(\theta_1 - \theta_2, \left[se(\hat{\theta}_1)\right]^2 + \left[se(\hat{\theta}_2)\right]^2\right)$ 

A z-statistic can be contrasted such that  $z = \frac{\widehat{\theta}_1 - \widehat{\theta}_2}{\sqrt{\left[se(\widehat{\theta}_1)\right]^2 + \left[se(\widehat{\theta}_2)\right]^2}} \sim N(0,1)$ , under the null

hypothesis of no treatment by subgroup interaction.

For k groups  $(k \ge 2)$ ,

let 
$$\widehat{\boldsymbol{\theta}} = (\widehat{\theta}_1, \widehat{\theta}_2, ..., \widehat{\theta}_k)$$
 and  $Var(\widehat{\boldsymbol{\theta}}) = diag([se(\widehat{\theta}_1)]^2, [se(\widehat{\theta}_2)]^2, ..., [se(\widehat{\theta}_k)]^2)$ .

A chi-square test (with degrees of freedom = k-1) can be constructed as

$$T = \left(C\widehat{\boldsymbol{\theta}}\right)'(CVC')^{-1}\left(C\widehat{\boldsymbol{\theta}}\right) \sim \chi_{k-1}^2$$

where C is a matrix of contrast such that

$$C = \begin{bmatrix} -1 & 1 & 0 & \dots & 0 & 0 \\ 0 & -1 & 1 & \dots & 0 & 0 \\ \dots & \dots & \dots & \dots & \dots & \dots \\ 0 & 0 & 0 & \dots & -1 & 1 \end{bmatrix}$$

